c Second primary malignancies (SPM) will be monitored as events of interest and must be reported as SAEs regardless of causal relationship to IP (POM or LD-dex), occurring at any time from the time of signing the ICD up to and including the long-term follow-up period. Documentation of the diagnosis of the SPM must be provided at the time of

- reporting as a SAE (eg, any confirmatory pathology, histology or cytology results, cytogenetics, flow cytometry, x-rays, or CT scans). For all subjects who develop SPMs, all corresponding diagnostic reports (eg, pathology, cytogenetics, flow cytometry) from the MM diagnosis confirmation performed at screening and from the diagnostic tumor samples obtained at SPM determination, will be required for SPM confirmation. If the SPM determination is made at an institution besides the study institution, every effort will be made to collect these reports when performed locally or at other institutions.
- d The measurement of height and weight will be performed at screening only.
  - e Assessment of hematology includes: WBC count with differential, ANC, ALC, HGB, HCT, platelet count, and MCV.
  - f Assessment of serum chemistry includes: calcium, albumin, total bilirubin, alkaline phosphatase, AST/SGOT, ALT/SGPT, GGT, sodium, potassium, BUN, creatinine, and LDH.
  - g Assessment of urinalysis includes: specific gravity, pH, glucose, bilirubin, protein, ketones, blood, and microscopic analysis [casts, bacteria, RBCs, and WBCs].
  - h The assessment will be performed using the Cockcroft-Gault formula for estimation of creatinine clearance (CrCl). CrCl will be determined based on a 24-hour urine collection. A 24-hour urine sample obtained as a standard of care assessment prior to informed consent can be utilized for this study if it was performed  $\leq 7$  days prior to the Screening Visit and meets the protocol requirements for collection and analysis.
  - i ECGs will be performed at Screening visit and as clinically indicated at the discretion of the treating physician during the study.
  - j Concomitant medications including: anti-infectious agents, growth factors, antithrombotics, bisphosphonates or other agents used for the treatment of myeloma-associated bone disease, and transfusions.

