### ***Laboratory Assessments for Safety Parameters***

With the exception of pregnancy tests, all laboratory assessments for safety parameters will be performed and reviewed by the central laboratory; however, tests that may result in dose interruption and/or modification should also be performed locally to allow for treatment related decisions during subject visits. Results from local laboratories will not be collected, unless specifically requested by the sponsor in which case they may be entered into an unscheduled visit on the eCRF. At Study Day 1 subject must meet eligibility criteria based on local or central lab results prior to initiating study therapy.

If screening visit results are  $\leq 7$  days prior to enrollment, these laboratory assessments are not required to be repeated at Cycle 1 Day 1.

- **Hematology Laboratory Tests.** Hematology includes: white blood cell (WBC) count with differential, absolute neutrophil count (ANC), absolute lymphocyte count

(ALC), hemoglobin, hematocrit, platelet count, and mean corpuscular volume. Hematology will be performed at screening, on Day 1 of each cycle, and at treatment discontinuation.

- **Serum Chemistry Laboratory Tests.** Serum chemistry includes: calcium (corrected), albumin, total bilirubin, alkaline phosphatase, aspartate aminotransferase (AST)/serum glutamic oxaloacetic transaminase (SGOT), alanine aminotransferase (ALT)/serum glutamic pyruvic transaminase (SGPT), gamma glutamyl transferase (GGT), sodium, potassium, blood urea nitrogen, creatinine, and lactate dehydrogenase. Serum chemistry labs will be performed at screening, on Day 1 ( $\pm$  3 days) of every cycle, and at treatment discontinuation. If PD is noted based on corrected serum calcium level, a repeat serum chemistry test should be performed as soon as possible to confirm PD.
- **Infectious Tests.** Human immunodeficiency virus (HIV), Hepatitis A, Hepatitis B and Hepatitis C. Infectious testing will be performed at screening for Cohort C only.
- **Urinalysis.** Urinalysis includes: specific gravity, pH, glucose, bilirubin, protein, ketones, blood and microscopic analysis (casts, bacteria, red blood cells [RBCs], and WBCs). Urinalysis will be performed at screening, and at treatment discontinuation.
- **Estimation of Renal Function.** The assessment will be performed using the Cockcroft-Gault estimate of creatinine clearance (CrCl).

*Cockcroft-Gault Formula* ([Cockcroft, 1976](#); [Luke, 1990](#))

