### Dose Modification and Interruption

Dosing interruptions and reductions are permitted throughout the study.

In the event of any dose reduction for POM, site staff must contact the Interactive Voice Response System (IVRS) to record the new dose level.

If the treatment has been interrupted and the next cycle is delayed beyond 28 days after Day 1 of the prior cycle, then Day 1 of the next cycle will be defined as the first day that treatment is resumed.

Subjects will be evaluated for AEs at each visit with the NCI-CTCAE (version 4.03) as a guide for the grading of severity.

- If POM is permanently discontinued, then the subject must be permanently discontinued from all study treatments.
- For Patients in Cohort B and Cohort C, if DARA is withheld or permanently discontinued, then POM, and LD-Dex dosing may be continued.
- If LD-dex dosing is withheld or permanently discontinued, then POM and DARA (for patients in Cohort B and Cohort C) dosing may be continued.

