### Dose Modification Instructions for Low-dose Dexamethasone

Dose Reductions for Low-dose dexamethasone-related Toxicities ([Table 4](#)) details instructions for LD-dex dose interruptions and reductions and [Table 5](#) outlines the dose reduction steps for LD-dex; however, the full product information and labeling contained in the current dex Package Insert should also be reviewed.

If LD-dex is held or permanently discontinued due to toxicity, POM, and (for patients in Cohort B and Cohort C) DARA may be continued.

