**Table 4: Dose Reductions for Low-dose Dexamethasone-related Toxicities**

Toxicity a	LD-dex Dose Modification
Dyspepsia = Grade 1-2	Maintain dose and treat with histamine (H2) blockers or equivalent. Decrease by one dose level if symptoms persist.
Dyspepsia ≥ Grade 3	Withhold dose until symptoms are controlled. Add H2 blocker or equivalent and decrease one dose level when dose restarted.
Edema ≥ Grade 3	Use diuretics as needed and decrease dose by one dose level.
Confusion or mood alteration ≥ Grade 2	Withhold dose until symptoms resolve. When dose restarted, decrease dose by one dose level.
Muscle weakness (steroid myopathy) ≥ Grade 2	Withhold dose until muscle weakness ≤ Grade 1. When dose restarted decrease dose by one dose level.
Hyperglycemia ≥ Grade 3	Decrease dose by one dose level. Treat with insulin or oral hypoglycemic agents as needed.
Acute pancreatitis	Discontinue subject from dex treatment regimen.
Other ≥ Grade 3 dex-related adverse events	Stop dex dosing until the adverse event resolves to ≤ Grade 2. Decrease by one dose level when dex dosing is resumed.

a If recovery from toxicities is prolonged beyond 14 days, then the dose of dex will be decreased by one dose level when dose is restarted.

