## **11. ADVERSE EVENTS**

### **11.1. Monitoring, Recording and Reporting of Adverse Events**

An AE is any noxious, unintended, or untoward medical occurrence that may appear or worsen in a subject during the course of a study. It may be a new intercurrent illness, a worsening concomitant illness, an injury, or any concomitant impairment of the subject's health, including laboratory test values (as specified by the criteria in Section 11.3, regardless of etiology. Any worsening (ie, any clinically significant adverse change in the frequency or intensity of a pre-existing condition) should be considered an AE. A diagnosis or syndrome should be recorded on the AE page of the eCRF rather than the individual signs or symptoms of the diagnosis or syndrome.

Abuse, withdrawal, sensitivity or toxicity to an investigational product should be reported as an AE. Overdose, accidental or intentional, whether or not it is associated with an AE should be reported on the overdose CRF. (See Section 8.3 for the definition of overdose.) Any sequela of an accidental or intentional overdose of an investigational product should be reported as an AE on the AE CRF. If the sequela of an overdose is an SAE, then the sequela must be reported on an SAE report form and on the AE CRF. The overdose resulting in the SAE should be identified as the cause of the event on the SAE report form and CRF but should not be reported as an SAE itself. In the event of overdose, the subject should be monitored as appropriate and should receive supportive measures as necessary. There is no known specific antidote for pomalidomide, daratumumab, or dexamethasone overdose. Actual treatment should depend on the severity of the clinical situation and the judgement and experience of the treating physician. All subjects will be monitored for AEs during the study. Assessments may include monitoring of any or all of the following parameters: the subject's clinical symptoms, laboratory, pathological, radiological or surgical findings, physical examination findings, or other appropriate tests and procedures.

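### No blood glucose is scheduled at any visit, although every cohort starts weekly dexamethasone and Table 4 sets a dose reduction for Grade 3 or higher hyperglycemia

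*Combined protocol and SAP*

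**What the plan says.** Table 1, note f, defines the panel: "Assessment of serum chemistry includes: calcium, albumin, total bilirubin, alkaline phosphatase, AST/SGOT, ALT/SGPT, GGT, sodium, potassium, BUN, creatinine, and LDH". The serum chemistry item under Laboratory Assessments for Safety Parameters in Section 6 gives the same 12 analytes and ends "gamma glutamyl transferase (GGT), sodium, potassium, blood urea nitrogen, creatinine, and lactate dehydrogenase". Both put chemistry at screening, Day 1 of each cycle and treatment discontinuation.

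Glucose appears only as a urinalysis component (Table 1, note g), and "Urinalysis will be performed at screening, and at treatment discontinuation".

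Section 8.2 starts all cohorts on dexamethasone 40 mg (20 mg above age 75) on Days 1, 8, 15 and 22 of a 28-day cycle. For hyperglycemia of Grade 3 or higher, Table 4 instructs: "Decrease dose by one dose level. Treat with insulin or oral hypoglycemic agents as needed".

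Several general provisions bear on detection:
- Section 8.2: "Subjects will be evaluated for AEs at each visit with the NCI-CTCAE (version 4.03) as a guide for the grading of severity".
- Section 6, on local laboratories: "tests that may result in dose interruption and/or modification should also be performed locally to allow for treatment related decisions during subject visits". Local results are not collected unless the sponsor asks for them.
- Section 11.1, on AE monitoring, including laboratory findings: "Assessments may include monitoring of any or all of the following parameters".
- Section 8.2, on dexamethasone: "the full product information and labeling contained in the current dex Package Insert should also be reviewed".
- Section 11.3 makes a laboratory abnormality an AE if it leads to discontinuation, needs treatment or a dose change, or is judged clinically important.

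**The concern.** The protocol contains a dose rule for a toxicity that is recognised by a blood measurement, but it never schedules that measurement. The main hematologic triggers in Table 2, neutrophils and platelets, are both in the hematology panel drawn on Day 1 of every cycle. Hyperglycemia has no counterpart.

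Two things are at stake. First, asymptomatic hyperglycemia on weekly dexamethasone may go unseen, so the Table 4 reduction may not be applied when it should be. Second, without a pre-treatment value, undiagnosed pre-existing hyperglycemia cannot be separated from hyperglycemia that emerges on treatment. Section 10.7 defines a treatment-emergent event by comparison with the pre-treatment state, so this bears on the secondary objective, safety. Glucose also cannot enter the graded laboratory and shift summaries if it is not collected.

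**Working it through.** The protocol states no figure to reproduce. The check sets the schedule beside the dose rule and counts.

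**Scheduled glucose measurements per subject** (Table 1 with notes f and g; Section 6)

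| | Screening | Each treatment cycle | Discontinuation |
|---|---|---|---|
| Blood glucose | 0 | 0 | 0 |
| Urine glucose | 1 | 0 | 1 |

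**Exposure and contact, Cohort C, six cycles** (Section 8.2; Table 1)
- Dexamethasone doses: 6 × 4 = 24, over 6 × 28 = 168 days.
- Scheduled visits: Day 1 in 6 cycles = 6; Days 8, 15 and 22 in Cycles 1–2 = 3 × 2 = 6; Day 15 in Cycles 3–6 = 4. Total 6 + 6 + 4 = 16.
- Visits with a chemistry draw: 6, all Day 1. Visits with a scheduled blood glucose: 0.
- From Cycle 7: 1 scheduled visit per 4 dexamethasone doses.

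**Do other records fill the gap?**
- AE evaluation at visits finds symptomatic cases. Asymptomatic ones need a test.
- The sentence on local tests names no analyte and sets no schedule, and its results are not collected by default.
- The Section 11.1 wording is permissive, and the package-insert reference creates no study assessment.
- The collected concomitant drugs (Table 1, note j; Sections 6 and 9.1) are anti-infectives, growth factors, antithrombotics and bone agents. Insulin and oral hypoglycemic agents are not listed, so outside an AE record drug data do not help. Section 11.2.5 does require treatment to be reported once an AE exists.

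**Rough scale.** Section 1.2 reports 3% Grade 3/4 glucose intolerance in the phase 3 trial of pomalidomide plus dexamethasone 40 mg on Days 1, 8, 15 and 22. Assuming that rate held in Cohort C:
- expected cases: 20 × 0.03 = 0.6;
- chance of at least one: 1 − 0.97^20 = 0.46; chance of none: 0.54.

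These are all cases, not missed ones. Glucose intolerance may not equal hyperglycemia, how that trial tested for it is not stated, and lower grades are not quantified.

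**Who can still benefit.** Cohorts A and B are fully enrolled: 56 + 112 = 168 of about 188. New baselines are possible only in Cohort C, about 20 subjects. How many Cohort A or B subjects remain on treatment is not stated.

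**The case against.** The best counter-argument is that Table 4 is driven by adverse events and does not depend on a scheduled assay. It also has rules for acute pancreatitis and steroid myopathy, and neither chemistry list contains a pancreatic or muscle enzyme. On that reading, a toxicity rule without its own test is this protocol's normal pattern. Cohorts B and C are seen often in the first six cycles, and a glucose test fits the functional description in the local-test sentence. Medical history and the review of prior medications at screening can identify known diabetes, exclusion criterion 11 bars a laboratory abnormality serious enough to preclude participation, and urine glucose is checked at screening. Finally, leaving untreated low-grade values out of the AE record is the Section 11.3 rule for every analyte.

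Much of this stands. It confines the gap to undetected, untreated or lower-grade hyperglycemia and, at baseline, to undiagnosed cases that the urine test does not reveal. It is also right that only scheduled values are zero, since sites may test locally, and that adding glucose would not turn low-grade values into AEs.

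It does not remove the gap. Pancreatitis and myopathy usually declare themselves by symptoms; raised glucose often does not. None of the safeguards schedules a blood glucose. In the local-test sentence, the word also can be read as covering only tests already done centrally, and glucose is not among those.

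**Conclusion.** The point holds and is minor. The plan schedules no blood glucose at baseline, on treatment or at discontinuation, while every cohort starts weekly dexamethasone under a rule that calls for dose reduction at Grade 3 or higher hyperglycemia. The consequence is incomplete safety ascertainment and no baseline, chiefly for the roughly 20 Cohort C subjects. Symptomatic, treated or dose-changing cases are already captured.

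The number of missed cases cannot be derived from the protocol. The 0.6 expected severe cases rest on carrying a 3% rate over from another trial and indicate scale only. Section 10.7 promises shift tables only for a selection of laboratory results, so omitting glucose breaks no stated commitment.

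**What to change.** - Add serum glucose to Table 1, note f, and to the Section 6 chemistry list, at screening, Day 1 of each cycle (before that day's dexamethasone) and treatment discontinuation. Apply this to Cohort C and to any Cohort A or B subject still on treatment.
- Name glucose in the Section 6 sentence on local tests, so that a result is available when the dose is decided.
- Include glucose in the Cohort C laboratory shift tables.
- Leave Table 4 as it is. Do not retrieve past local values for Cohorts A and B; they would over-represent subjects tested for cause.

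The cost is a text change to two lists and one sentence, one more analyte on blood already drawn, and one more table, with no new visit. If all 20 Cohort C subjects complete six cycles, central assays per subject are 1 + 6 + 1 = 8, or 1 + 5 = 6 if Cycle 1 Day 1 is waived (screening results within 7 days) and discontinuation has not yet occurred. That gives 120 to 160 assays in all. Local testing on every Day 1 adds up to 6 × 20 = 120.

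The limitation is timing. A pre-dose Day 1 sample falls nominally 29 − 22 = 7 days after the previous dose. In Cycles 1–2, with both ±3-day windows, the interval runs from (29 − 3) − (22 + 3) = 1 to (29 + 3) − (22 − 3) = 13 days, and longer if a cycle is delayed. Transient post-dose peaks may be missed, so the change improves detection without making it complete.

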## 6. PROCEDURES

### Study Entry

Prior to screening, subjects must sign an informed consent document. All screening assessments must be completed within 28 days prior to start of Cycle 1, with the exception of the skeletal survey, which may be performed within 60 days prior to initiation of study treatment, with the approval of sponsor.

Confirmation of diagnosis (including date of confirmed initial diagnosis and, if available, myeloma stage at time of initial diagnosis per the Salmon-Durie Criteria and/or the International Staging System [[Appendix H](#)]), medical history, prior cancer and surgical history, and review of prior medications should be documented during the screening period. All prior radiotherapy, surgeries, and anti-myeloma therapies must be recorded in the electronic case report form (eCRF), including approximate dates for each therapy and the date of progression for each regimen. Results for any local cytogenetic testing (prefer fluorescence in situ *hybridization* [FISH] results), if available, as part of medical history, will be collected in the eCRF. See [Table 1](#) (Table of Events) for a complete list of the required assessments during screening.

If the subject's safety and efficacy laboratory assessments performed at screening are within 7 days of enrollment into the study, they do not need to be repeated at Cycle 1 Day 1 and can be used as baseline results. The start of study drug dosing is designated as Cycle 1 Day 1. A 14-day wash-out period is required for any prior anti-myeloma therapy before study treatment is initiated.

### Safety Assessments

#### *Adverse Events*

All AEs should be assessed starting after the subject signs the informed consent document (ICD) until 28 days after treatment discontinuation. Adverse events that lead to study discontinuation should be followed until resolution or stabilization.

#### *Serious Adverse Events*

Serious adverse events, regardless of relationship to the IP (POM, DARA, or dex), that occur from the time the subject signs the ICD to at least 28 days after treatment discontinuation and those made known to the investigator at any time thereafter that are suspected of being related to the IP (POM, DARA, or dex) must be reported to Celgene Drug Safety within 24 hours of the investigator's knowledge of the event.

#### *Second Primary Malignancies*

Second primary malignancies will be monitored every 3 months for up to 5 years after the last subject is enrolled in each respective cohort, as events of interest and must be reported as SAEs. This includes any SPM, regardless of causal relationship to the IP (POM, DARA, or dex), occurring at any time from the time of signing the ICD up to and including the long-term follow-up period. Events of SPM are to be reported using the SAE report form and must be considered an "Important Medical Event" even if no other serious criteria apply; these events must also be documented in the appropriate page(s) of the eCRF and subject's source documents.

Documentation of the diagnosis of the SPM must be provided at the time of reporting as a SAE

eg, any confirmatory pathology, histology or cytology results, cytogenetics, flow cytometry, x-rays, or computed tomography scans (CT scans). For all subjects who develop SPMs, all corresponding diagnostic reports (eg, pathology, cytogenetics, flow cytometry) from the MM diagnosis confirmation performed at screening and from the diagnostic tumor samples obtained at SPM determination, will be required for SPM confirmation.

For SPMs diagnosed at another institution, (outside of the investigational site) sites will be required to make every effort to obtain these reports for SPM confirmation.

### ***Prior and Concomitant Medications and Procedures***

The following prior and concomitant therapies will be collected and recorded in the subject's eCRF: Anti-infectious agents, antithrombotics, growth factors, and bisphosphonates or other agents used for the treatment of myeloma-associated bone disease. Any procedures performed, including transfusions, after the subject signs the ICD until 28 days after treatment discontinuation will be collected and recorded in the subject's eCRF. Drugs known to prolong the QT corrected (QTc) interval should be avoided unless deemed medically necessary. See [Appendix G](#) for a comprehensive list of drugs which are known to prolong QTc.

### ***Venous Thrombotic Events Assessment and Monitoring***

All prior venous thromboembolisms (VTEs) and pulmonary embolisms (PEs) that occurred will be collected with complete medical history during the screening period. The VTE assessment will be performed on Day 1 of every cycle starting at Cycle 1, and at treatment discontinuation. Subjects who develop symptomatic deep vein thrombosis will be assessed and diagnosed objectively by Doppler ultrasonography or a comparable method. See [Appendix A](#) for deep vein thrombosis (DVT) and PE diagnostic algorithms.

### ***Measurement of Height and Weight***

Measurement of height and weight will be performed at screening only.

### ***Electrocardiogram***

For subjects enrolled in Cohort A, electrocardiogram (ECG) (12-lead) monitoring will be performed at the Screening visit and as clinically indicated at the discretion of the treating physician during the study. All ECGs will be performed and reviewed locally.

### ***Laboratory Assessments for Safety Parameters***

With the exception of pregnancy tests, all laboratory assessments for safety parameters will be performed and reviewed by the central laboratory; however, tests that may result in dose interruption and/or modification should also be performed locally to allow for treatment related decisions during subject visits. Results from local laboratories will not be collected, unless specifically requested by the sponsor in which case they may be entered into an unscheduled visit on the eCRF. At Study Day 1 subject must meet eligibility criteria based on local or central lab results prior to initiating study therapy.

If screening visit results are  $\leq 7$  days prior to enrollment, these laboratory assessments are not required to be repeated at Cycle 1 Day 1.

- **Hematology Laboratory Tests.** Hematology includes: white blood cell (WBC) count with differential, absolute neutrophil count (ANC), absolute lymphocyte count

(ALC), hemoglobin, hematocrit, platelet count, and mean corpuscular volume. Hematology will be performed at screening, on Day 1 of each cycle, and at treatment discontinuation.

- **Serum Chemistry Laboratory Tests.** Serum chemistry includes: calcium (corrected), albumin, total bilirubin, alkaline phosphatase, aspartate aminotransferase (AST)/serum glutamic oxaloacetic transaminase (SGOT), alanine aminotransferase (ALT)/serum glutamic pyruvic transaminase (SGPT), gamma glutamyl transferase (GGT), sodium, potassium, blood urea nitrogen, creatinine, and lactate dehydrogenase. Serum chemistry labs will be performed at screening, on Day 1 ( $\pm$  3 days) of every cycle, and at treatment discontinuation. If PD is noted based on corrected serum calcium level, a repeat serum chemistry test should be performed as soon as possible to confirm PD.
- **Infectious Tests.** Human immunodeficiency virus (HIV), Hepatitis A, Hepatitis B and Hepatitis C. Infectious testing will be performed at screening for Cohort C only.
- **Urinalysis.** Urinalysis includes: specific gravity, pH, glucose, bilirubin, protein, ketones, blood and microscopic analysis (casts, bacteria, red blood cells [RBCs], and WBCs). Urinalysis will be performed at screening, and at treatment discontinuation.
- **Estimation of Renal Function.** The assessment will be performed using the Cockcroft-Gault estimate of creatinine clearance (CrCl).

*Cockcroft-Gault Formula* ([Cockcroft, 1976](#); [Luke, 1990](#))

$\text{CrCl (mL/min)} = (140 - \text{age}) (\text{weight [kg]}) / 72 (\text{serum creatinine [mg/dL]})$ ; for females, the formula is multiplied by 0.85.

CrCl will be determined based on a 24-hour urine collection at the Screening visit. A 24-hour urine sample obtained as a standard of care assessment prior to informed consent can be utilized for this study if it was performed  $\leq 7$  days prior to the Screening Visit.

Estimation of renal function will be performed at Screening only.

